	6.1 Published References.....	20
	6.2 Unpublished References	22

Statistical Analysis Plan Template For Observational Studies

Boehringer Ingelheim
Protocol c14668275-02

Statistical Analysis Plan

LIST OF ABBREVIATIONS

ADR	Adverse Drug Reaction
AE	Adverse Event
BI	Boehringer Ingelheim
CRA	Clinical Research Associate
CRF	Case Report Form
CUP	Compassionate Use Program
EAP	Early Access Program
ECOG	Eastern Cooperative Oncology Group
eCRF	Electronic Case Report Form
EDC	Electronic Data Capture
EGFR	Epidermal Growth Factor Receptor
EU	European Union
FAS	Full Analysis Set
FDA	Food and Drug Administration
IEC	Independent Ethics Committee
IRB	Institutional Review Board
NIS	Non-Interventional Study
NSCLC	Non-Small Cell Lung Cancer
PD	Progressive Disease
PFS	Progression-Free Survival
PS	Performance Score
RDC	Remote Data Capture
RWD	Real-World Data
SAP	Statistical Analysis Plan
SD	Standard Deviation
TLF	Tables, Listings and Figures
TKI	Tyrosine Kinase Inhibitors
US	United States of America

Statistical Analysis Plan Template For Observational Studies

Boehringer Ingelheim
Protocol c14668275-02

Statistical Analysis Plan

1 INTRODUCTION

Metastatic epidermal growth factor receptor (EGFR)-mutant lung cancers are sensitive to first- and second-generation EGFR tyrosine kinase inhibitors (TKIs) gefitinib, erlotinib and afatinib (P14-03814).

Afatinib is an irreversible ErbB family blocker and the first marketing approval of afatinib was granted on 12 Jul 2013 in the United States of America (US) – trade name Gilotrif[®] – for the indication of first-line treatment of patients with metastatic non-small cell lung cancer (NSCLC) whose tumours have EGFR exon 19 deletions or exon 21 (L858R) substitution mutations as detected by an Food and Drug Administration (FDA) - approved test. It was approved in the European Union (EU) on 25 Sep 2013 (trade name Giotrif[®]) as monotherapy indicated for the treatment of EGFR TKI-naïve adult patients with locally advanced or metastatic NSCLC with activating EGFR mutation(s). In total, marketing authorisation for Gi(l)otrif[®] has been granted in 70 other countries world-wide as of today (c01802941-10).

On the clinical trials LUX-Lung 3 (P13-07382), LUX-Lung 6 (P14-00758) and LUX-Lung 7 (P16-04350), afatinib (Gi(l)otrif[®]) showed a median progression-free survival (PFS) of 11.1, 11.1 and 13.6 months, respectively, for patients with EGFR common mutations (Del19 and L858R) treatment-naïve. Time to treatment failure in LUX-Lung 7 was 13.7 months. Eventually, resistance develops for most patients and the most common mechanism of resistance to EGFR TKIs (>50%) is the emergence of a second-site EGFR-mutation, the T790M (R15-6101, P09-09950).

Explorative analysis of LUX-Lung 7 showed a median overall survival of not being reached for patients who started with afatinib (Gi(l)otrif[®]) and received subsequently osimertinib or olmutinib (follow-up period of 42.6 months) indicating a long-time benefit from this sequence (P16-13901).

Osimertinib, a third generation EGFR TKI, was approved for patients whose tumours have developed the EGFR T790M mutation by several countries. The first marketing approval of osimertinib was granted on 13 Nov 2015 in the US (R16-5838). The EU and Japan also gave a similar approval on 03 Feb 2016 and 29 Mar 2016 separately (P16-15191, P16-15190).

In addition, osimertinib has been studied in the first-line treatment in an expansion cohort from AURA trial, whose reported result looked promising (median PFS for the 80 mg cohort had not yet been reached but for the 160 mg cohort was shown to be 19.3 months) (R16-5840). Confirmation of these results in a phase III randomized trial is still needed to define the role of osimertinib in the treatment of patients with EGFR mutation-positive. FLAURA is comparing osimertinib to either gefitinib or erlotinib in EGFR mutant NSCLC treatment naïve patients and results are expected to be presented during 2017 (R16-5841).

Statistical Analysis Plan Template For Observational Studies

Boehringer Ingelheim
Protocol c14668275-02

Statistical Analysis Plan

Whether osimertinib will extend PFS versus available therapies if used as front-line therapies remains unknown. Investigating in this real-world data (RWD) study the time from start of first-line afatinib (Gi(l)otrif[®]) until the end of second-line osimertinib in this study provides insights on treatment sequence that can inform on the most beneficial treatment sequence for the patients.

The data analysed on this study will be collected from medical records of patients treated with afatinib (Gi(l)otrif[®]) as the first-line treatment followed by osimertinib in case the T790M resistance mutation was developed.

This statistical analysis plan (SAP) provides the description of the variables to be collected and the methodology on which the analysis will be based.

This SAP is based upon the following study documents:

- Study Protocol, Version 2.0 (September 11, 2017)
- Case Report Form (CRF), Version 3.0 (February 06, 2018)

2 STUDY OBJECTIVES

Primary objective:

To determine the time on treatment of afatinib (Gi(l)otrif[®]) as first-line therapy in patients with EGFR mutation-positive NSCLC followed by osimertinib in case the T790M resistance mutation was developed in real-world setting. Time on treatment is defined from the start of the first-line treatment until the end of the second-line treatment or death date by any cause.

Secondary objective:

To collect data on acquired resistance mechanism to osimertinib.

3 STUDY DESIGN

This is a non-interventional, multi-country, multi-centre cohort study based on existing data from medical records of patients with EGFR mutation-positive advanced NSCLC treated with afatinib (Gi(l)otrif[®]) as the first-line treatment followed by osimertinib in case the T790M resistance mutation was developed.

In total, at least 190 eligible patients are planned to be enrolled to this study.

Key study outcome:

The time on treatment with afatinib (Gi(l)otrif[®]) followed by osimertinib.

Statistical Analysis Plan Template For Observational Studies

Boehringer Ingelheim
Protocol c14668275-02

Statistical Analysis Plan

It is planned that around 65 study centres in 11 countries will be participating in this non-interventional study (NIS) and at least 190 consecutive eligible patients will be enrolled to the study. Every patient who fulfils inclusion and exclusion criteria and agree to participate in the study (if a written informed consent is required for this NIS by local regulation and legal requirement) will be selected until the required sample size is achieved. Deceased patients should be enrolled whenever possible.

Recruiting of patients for this study is competitive, i.e., recruitment will stop at all centres when it is determined that a sufficient number of patients have been enrolled.

3.1 Identification of Analysis Population

3.1.1 Site selection

Sites in countries meeting the criteria below:

- Sites in countries with afatinib (Gi(l)otrif[®]) launch dates prior to 01 Jan 2015 and known to prescribe afatinib (Gi(l)otrif[®]) on a regular basis;
- Osimertinib used in patients with EGFR T790M mutation-positive NSCLC within an early access program/ compassionate use program (EAP/CUP) or regular clinical practice; osimertinib provided via a clinical trial is not permitted.

3.1.2 Inclusion criteria

1. Patients with EGFR mutation-positive advanced NSCLC
2. The tumour harbours common EGFR mutations (Del19, L858R) at start of first-line treatment
3. Patients who initiated second-line osimertinib treatment for acquired T790M mutation at least 10 months prior to data entry, AND who were treated with afatinib (Gi(l)otrif[®]) in the first-line
4. Patients treated with osimertinib within an EAP/CUP or regular clinical practice
5. Age \geq 18 years
6. Signed and dated written informed consent per regulations (Exemption of a written informed consent for NIS based on existing data in countries per local regulations and legal requirements)

3.1.3 Exclusion criteria

1. Patients who received drug(s) other than osimertinib as the second-line treatment and/or patients who received drug(s) other than afatinib (Gi(l)otrif[®]) as the first-line treatment
2. Patients with active brain metastases at start of treatment (either afatinib/Gi(l)otrif[®] or osimertinib)

Patients treated with afatinib (Gi(l)otrif[®]) and/or osimertinib in interventional trials are excluded to ensure the non-interventional setting of this study. Real-world studies such as ASTRIS are not affected by this exclusion (R17-0754). The threshold of start of

Statistical Analysis Plan Template For Observational Studies

Boehringer Ingelheim
Protocol c14668275-02

Statistical Analysis Plan

osimertinib at least 10 months prior to data entry was chosen based on the median PFS result of AURA-3 (R17-0221) to avoid early censoring and enable collection of mature data on adverse drug reactions (ADRs) and treatment duration. All patients fulfilling inclusion and exclusion criteria from a site will be entered to avoid bias.

3.2 Full Analysis Set

The full analysis set (FAS) includes all patients who were enrolled into the study, met all inclusion criteria and did not meet any exclusion criteria and provided a written and signed informed consent (if a written informed consent is required for this NIS by local regulation and legal requirement). The FAS will be used for all the analyses performed during this study.

3.3 Study Groups/Cohorts

3.3.1 Afatinib/Osimertinib Group

The afatinib/osimertinib group consists of all patients in FAS. This will be the only group in this study.

3.3.2 Comparison Group

This study has no comparator group.

3.4 Definition of Subgroups

Selected analyses will also be provided for some of the following subgroups:

- Ethnicity: Asia (Japan, Singapore and Taiwan) vs Non-Asia (Austria, Germany, Italy, Israel, Slovenia, Spain, Canada and US)
- Race: Asian vs Black or African American vs White (the other races – American Indian or Alaska Native, Native Hawaiian or Other Pacific Islander and Other – will not be included in this subgroup)
- EGFR mutation at start of Afatinib: Del19 vs L858R
- Gender: Male vs Female
- Brain metastases at start of Afatinib: Presence vs Absence
- Brain metastases at any time: Presence vs Absence
- Age group 1 at start of Afatinib: <65 years vs ≥65 years
- Age group 2 at start of Afatinib: <75 years vs ≥75 years
- ECOG at start of Afatinib: Low ECOG (0 and 1) vs High ECOG (2, 3, 4 and 5)
- Data source: Cardinal Health vs Other Clinical Sites

Statistical Analysis Plan Template For Observational Studies

Boehringer Ingelheim
Protocol c14668275-02

Statistical Analysis Plan

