3.5 Study Outcomes

3.5.1 Data Collected

The following data will be collected from medical records and will be recorded in the electronic case report form (eCRF) by investigators (or designees) during the study period:

- Informed consent
- Demographics: age at start of afatinib (Gi(l)otrif[®]) treatment, gender, ethnicity and race
- Type of mutations at initial diagnosis
- Stage of disease (IIIb or IV) at start of afatinib (Gi(l)otrif[®]) treatment
- Sites of metastases at start of afatinib (Gi(l)otrif[®]) treatment
- Eastern Cooperative Oncology Group (ECOG) performance score (PS) (if available) at start of afatinib (Gi(l)otrif[®]) treatment
- Body weight and height at start of afatinib (Gi(l)otrif[®]) treatment
- Date of start and end of afatinib (Gi(l)otrif[®]) treatment
- Starting dose of afatinib (Gi(l)otrif[®])
- Afatinib (Gi(l)otrif[®]) dose modification(s) and respective date(s)
- Reason for discontinuation of afatinib (Gi(l)otrif[®]) treatment (e.g. progressive disease (PD), adverse event (AE))
- Type of mutations at start of osimertinib treatment
- Sites of metastases at start of osimertinib treatment
- ECOG PS (if available) at start of osimertinib treatment
- Type of mutations at stop of osimertinib if available (EGFR mutations: T790M, C797S [if positive: in cis or in trans], Del19, L858R, other EGFR sensitizing mutation (to be specified), non-EGFR: to be specified) (R16-1552, P15-11024)
- If osimertinib was provided within an EAP/CUP or prescribed as clinical practice
- Date of start and end of osimertinib treatment
- Starting dose of osimertinib
- Osimertinib dose modification(s) and date(s)
- Reason for discontinuation of osimertinib treatment (e.g. PD, AE)
- Subject status at data entry completion
- Date of death (if available) / Date patient was last known to be alive (if available)
- Date of consent withdrawal (if applicable)
- All ADRs (independently from the outcome) and AEs with fatal outcome with respective start and end dates, severity, outcome, seriousness and relationship to afatinib (Gi(l)otrif[®])

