5.5.2 Second Line Treatment – Osimertinib

The frequency of the different types of mutations at start and stop of osimertinib – Del19, L858R, both, T790M and other mutations – will be summarized. T14.2.2.1

This analysis will be repeated for the Race subgroup. T14.2.2.2

The type of mutations at stop of osimertinib will be analysed according to section 5.6.2.

The number and percentage of patients with metastases at start of osimertinib will be provided by site of metastases. T14.2.2.3

This analysis will be repeated for the Race subgroup. T14.2.2.4

The ECOG PS at start of osimertinib will be summarized in terms of number and percentage of patients with ECOG PS equal to 0, 1, 2, 3, 4, 5 or missing. T14.2.2.5

This analysis will be repeated for the Race subgroup. T14.2.2.6

The number and percentage of patients that, for treatment with osimertinib, used the regular clinical practice program or did it through EAP/CUP will be summarized. T14.2.2.7

The starting osimertinib dose will be summarized through descriptive statistics. T14.2.2.8

This analysis will be repeated for the Race subgroup. T14.2.2.9

The frequency and number of dose reductions and increases, and both of osimertinib and the reason for change will also be summarized. T14.2.2.10

The frequency of treatment interruptions and the frequency and reason for treatment discontinuation will be provided. T14.2.2.11

Statistical Analysis Plan Template For Observational Studies

Boehringer Ingelheim
Protocol c14668275-02

Statistical Analysis Plan

A summary analysis of patients for which metastases were developed or disappeared from start of Afatinib to start of Osimertinib will be provided. T14.2.2.12

A shift table of ECOG PS from start of Afatinib to start of Osimertinib will be displayed. T14.2.2.13

By-patient listings with the following information will be provided:

- Type of mutations, site of metastases and ECOG PS at start of osimertinib and the program used for treatment with osimertinib. L16.2.6.3

- Start and end date of initial dose and the respective dose, start and end date of all modified doses and the respective doses and the reasons for dose modification(s); reason for treatment discontinuation. L16.2.6.4

- Type of mutations at stop of osimertinib, before classification and categorization. L16.2.6.5

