5.6 Statistical methods

5.6.1 Analysis of the Primary Outcome

The primary outcome is time on treatment, which is defined as time in months from the start date of afatinib (Gi(l)otrif[®]) treatment – ‘start date of initial dose’ for First Line Treatment – to the end date of osimertinib treatment – maximum between ‘end date of initial dose’ and the last ‘end date of dose modification’ for Second Line Treatment – or death date due to any cause – ‘date of death’.

$$\text{Time on treatment (months)} = \text{time on treatment (days)} / 30.4375$$

Time on treatment will be analysed using Kaplan-Meier method, and the median along with two-sided 90% confidence interval will be displayed using the Greenwood’s formula for estimation of standard errors.

The primary outcome will be analysed in SAS using the LIFETEST procedure as follows:

```
proc lifetest data=mydata alphaqt=0.1  
  plots=survival(atrisk failure);  
  time t*event(0);  
run;
```

where **alphaqt** specifies the 90% confidence interval; the **t** variable is the time in months from the start date of afatinib (Gi(l)otrif[®]) treatment to the end date of osimertinib treatment or death; and the **event** variable specifies the subjects for which the whole information is present (=1) or were censored (=0). T14.2.3.1

The time on treatment (afatinib, osimertinib and total) will be summarized through descriptive statistics and survival plots will be provided. F14.2.3.5

Statistical Analysis Plan Template For Observational Studies

Boehringer Ingelheim
Protocol c14668275-02

Statistical Analysis Plan

Both tables and plots will be repeated for the following subgroups: Ethnicity, Race, EGFR mutation, Gender, Brain metastases at start of Afatinib, Brain metastases at any time, Age group 1, Age group 2, ECOG and Data Source. T14.2.3.2
F14.2.3.6
T14.2.3.8
F14.2.3.10

For the subgroup analyses, the log-rank test results will be provided. These results may be obtained introducing the strata statement in the LIFETEST procedure as follows: T14.2.3.12
F14.2.3.14

```
proc lifetest data=mydata alphaqt=0.1  
  plots=survival(atrisk failure);  
  time t*event(0);  
  strata subgroup;  
run;
```

For the total time on treatment, the information on the number and percentage of censored patients will also be summarized. T14.2.3.3

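### The any-time brain-metastasis subgroup can be settled only at osimertinib start, yet it is a fixed stratum for time counted from afatinib start

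*SAP*

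**What the plan says.** Section 3.4 lists two brain-metastasis subgroups. One is anchored at afatinib start, as are EGFR mutation, both age groupings and ECOG. The other, "Brain metastases at any time: Presence vs Absence", has no start, end or assessment point.

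Section 3.5.1 lists metastatic sites at afatinib start and again as "Sites of metastases at start of osimertinib treatment". It lists no later assessment and no onset date. Section 5.5.2 expects change between the two starts: it plans a summary (T14.2.2.12) of patients whose "metastases were developed or disappeared from start of Afatinib to start of Osimertinib".

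Section 5.6.1 promises that "The time on treatment (afatinib, osimertinib and total) will be summarized through descriptive statistics and survival plots will be provided", and repeats these tables and plots for the subgroups, including "Brain metastases at start of Afatinib, Brain metastases at any time, Age group 1, Age group 2, ECOG and Data Source". It adds: "For the subgroup analyses, the log-rank test results will be provided". The sample code puts the subgroup in the strata statement, and its time "variable is the time in months from the start date of afatinib" to the end of osimertinib or death. No landmark, time-dependent method or caveat is given.

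Two eligibility rules matter. Section 3.1.2 requires every patient to have started osimertinib. Section 3.1.3 excludes "Patients with active brain metastases at start of treatment", for either drug.

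**The concern.** A fixed stratum in a Kaplan-Meier or log-rank comparison should be known at time zero. On the listed data, the any-time grouping differs from the afatinib-start grouping only through brain lesions first recorded at osimertinib start, when the afatinib period is over. Patients are then split at afatinib start by a status that a longer or shorter afatinib period may itself have produced.

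At stake are the total-time curves and p-value and the afatinib-time plots for this one grouping. A reader could take a difference created by the way the groups were formed for an effect of brain metastases, and a real adverse effect could be masked.

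**Working it through.** **1. The plan's own figure.** Section 5.9 gives 171 patients, raised for 10% censoring: 171 / 0.9 = 190. With 171 exponential times and a median of 24 months, the simulated chance of a 90% interval no wider than 10 months is 0.797 with log-log limits, against 0.80 stated (0.72 with linear limits). It reproduces, and this point does not touch it.

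**2. When each grouping is known.**

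| Grouping | Known at | Total or afatinib time (zero = afatinib start) | Osimertinib time (zero = osimertinib start) |
|---|---|---|---|
| Afatinib-start | afatinib start | known at zero | known at zero |
| Any-time | osimertinib start | not known at zero | known at zero |

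**3. How duration can drive membership.** Assume new lesions arise at 10% per year without ending afatinib. The chance of reclassification after *a* months is 1 − 0.9^(a/12): 5.1% at 6 months and 19% at 24 months.

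**4. How many patients move.** Take an exponential afatinib phase with median 11.5 months (scaling explained in step 5) and 10% with brain metastases at afatinib start (assumed).
- Hazard of stopping afatinib: ln 2 / 11.5 = 0.0603 per month.
- Onset hazard: −ln 0.9 / 12 = 0.00878 per month.
- Share with a new lesion among those without one at afatinib start: 0.00878 / (0.00878 + 0.0603) = 0.127.
- Of 190: 190 × 0.9 × 0.127 ≈ 22.
- If the section 3.1.3 exclusion removes half of these patients and others are enrolled instead: 0.9 × 0.127 / 2 = 0.057, and 190 × 0.057 / (1 − 0.057) ≈ 12.

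**5. Log-rank rejection with no true effect** (two-sided 5%, n = 190). From section 5.9: phase medians 13.7 and 10.1 months, total median 24, 10% censoring. Two exponential phases with the unscaled medians give a total median of 28.7, so both were multiplied by 0.837 (11.5 and 8.5). Data entry was uniform from 10 months (section 3.1.2) to 63 months (set to give about 10% censoring) after osimertinib start. Onset rate, baseline prevalence, share removed and phase shape are assumptions.

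Lesions accumulating without ending afatinib, rejection on total time at onset 3/5/10/20% per year:

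| New-lesion patients removed by 3.1.3 | Exponential afatinib phase | Weibull, shape 1.5 |
|---|---|---|
| none | 16/31/65/95% | 7/10/19/45% |
| half | 9/14/37/77% | 6/6/10/27% |
| three quarters | 6/8/19/53% | 6/5/6/13% |

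With Weibull shape 2 and half or more removed, it is about 5–7% up to 10% onset and at most about 11% at 20%. Repeat runs differ by a few points (the 37% cell ranged from 35 to 39%).

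Other mechanisms (exponential phase, 10% onset, half removed):
- New lesions a constant share of afatinib stops: 5–6%, no inflation.
- New lesions mainly at early stops: 22%, direction reversed.
- Half accumulating, half constant share: 13%.

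**6. The alternative.** The same grouping on time from osimertinib start rejected in about 4–7% of trials in every setting. The afatinib-start grouping on total time gave 5–9%. Its highest value came where three quarters were removed, because the exclusion itself then selects on afatinib duration.

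**The case against.** **Everyone reaches osimertinib, so there is no immortal time.** This is true as far as it goes: no event can precede classification in either group. It does not stop afatinib duration from influencing who is classed as present while also being part of the outcome.

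**The size rests on assumptions.** This stands. Section 5.9 assumes that total time is exponential and gives no distribution for either phase. Changing only the afatinib shape, at 10% onset with half removed, takes rejection from 35–39% to about 10% or 7%. The rows with none removed require every new lesion to be non-active at osimertinib start. A reader might infer from the 65% or 95% values that the planned p-value will be grossly inflated; the documents do not support that.

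**The SAP already offers a check.** This stands in part. T14.2.2.12 shows how many patients could move, if it is broken down by site. The osimertinib-time outputs for this grouping and the total-time outputs for the afatinib-start grouping give a comparison. A total-time difference absent from both would be a warning, but nothing tells the reader to look for it.

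**Only one definition is workable, and unseen forms may settle it.** On the listed data the workable reading is indeed lesions recorded at either start. The case report form and table shells are not at hand, so this remains an inference. If they hold later brain lesions, the missing window matters more: membership could then depend on osimertinib duration too.

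**Conclusion.** The point holds as a minor one. The grouping has no window and, on the listed data, is post-baseline; used as a fixed stratum from afatinib start, it can give a misleading comparison. How misleading cannot be determined: about 5% to 95% rejection at a nominal 5% if lesions accumulate at 3–20% per year, depending on onset rate, share excluded and shape, and about 5% if they are independent of afatinib duration. The direction can go either way.

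A reader might infer that the primary result is compromised. It is not: the whole-cohort median and the 190 patients do not use this grouping, and it is one of ten descriptive subgroup variables in a study without a comparator. The explicit code tests total time; no log-rank test is specified for afatinib time alone. Osimertinib-time outputs are sound for a grouping fixed at osimertinib start.

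**What to change.** - **Section 3.4:** define the any-time subgroup as brain metastases recorded at afatinib start or at osimertinib start. This closes the window whatever the case report form holds.
- **Section 5.6.1:** for this subgroup, run the Kaplan-Meier comparison and log-rank test on time from osimertinib start (a landmark analysis). The table and plot are already planned; the code needs only its time variable changed. No patient is lost, because section 3.1.2 requires osimertinib start. For total and afatinib time, use the planned afatinib-start subgroup.
- **If total-time output for the any-time subgroup is kept:** show it descriptively, without a log-rank p-value, and note that the grouping is post-baseline.

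A time-dependent analysis is not possible from the listed data, which hold no onset dates. The any-time grouping also appears in the censoring and resistance-mutation tables; these need only the definition.

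Cost: two or three lines and no new data. One descriptive subgroup loses its total-time and afatinib-time comparison, or at least its test.
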